7.0 Study Withdrawal/Discontinuation

Participants may decide to discontinue participation at any time during the study. If a patient voluntarily requests withdrawal from the trial, we request that the site investigator

elicit the reason for the withdrawal and provide documentation in the clinic record and complete the respective case report form. We will have a dedicated patient navigator on staff as well to help trace and re-engage all participants lost to follow-up, realizing that some may die or transfer their care and must be appropriately categorized. Those who drop out due to AEs or perceived AEs will be counseled by study physicians regarding their options and any potential risks for continuation. The site must invest time in trying to meet the needs of the patient and their caregivers in order to make the patient's participation a success. The patient's caregiver should provide the withdrawal in writing for the clinic record. All voluntary withdrawals must be communicated to the SOC located at Vanderbilt University Medical Center by completion of the case report form in REDCap and should be recorded in the participant's study binder onsite.

Principal Investigator-initiated Withdrawal

Investigators may discontinue any participant at their discretion, if in their professional opinion the participant's health, safety, and/or well-being is being threatened or at all jeopardized by continued participation in the study. The following circumstances require discontinuation of participants:

- 1. Withdrawal of assent to participate;
- 2. Parental withdrawal of consent to participate;
- 3. Study physician determines that continuation in the study would not be in the best interest of the participant, e.g., pregnancy;
- 4. Participant has experienced a serious and/or unanticipated adverse event.

Adverse events caused by participation in the study may necessitate modifications to the level of participation of a subject or discontinuation of participation in the study. Participants who discontinue early from the study will not be replaced. They will continue to receive medical care at the AKTH HIV clinic as per standard care.

8.0 Statistical Considerations

[figure not shown]
Specific Aim 1

Sample size justification: A screening sample size of 2,600 participants will yield sufficient sample size for randomization in Specific Aim 2 detailed below. With 2,600 persons screened for Aim 1, the prevalence of *APOL1* renal risk variants may be estimated with precision (half-length of the 95% confidence interval) equal to 0.02 or better. Assuming a microalbuminuria prevalence of 17.5% based on recent data obtained from HIV-positive adults (n ~ 460) screened at AKTH,¹¹⁰ where this study will take place, we will have 90% power to detect a relative risk of microalbuminuria of 1.37 or higher in participants with renal risk variants compared to participants without, and we anticipate that 1 in 4 participants will have renal risk variants. We estimate, based on our experience with our studies at this site, that enrollment for Aim 1 will take 12 months. In addition to analyzing *APOL1* risk as a binary high/low risk status, we will also examine relative risk of microalbuminuria with *APOL1* risk categorized based on the presence of 0, 1, or 2 alleles, as this will lead to an increased understanding of the risk associated with the presence of a single risk allele.

Statistical analysis plan: We will estimate the prevalence and associated 95% confidence interval of *APOL1* renal risk variants. We will test whether the presence of these variants is associated with log₁₀uACR or eGFR using Wilcoxon rank sum test. Multivariable linear regression for each of log₁₀uACR or eGFR will be used to adjust for potential confounders, including: sex, age, CD4+ cell count, viral load, and the presence/absence of specific comorbid medical conditions (hypertension, cardiovascular disease, diabetes mellitus, etc.). For linear regression, appropriate transformations of dependent variables will be used to satisfy modelling assumptions. To relax linearity assumptions, covariates will be modelled using restricted cubic splines.¹³⁵ Modified

Poisson regression adjusted for similar variables, will be used to assess associations with prevalent CKD, microalbuminuria, and reduced eGFR (< 60 mL/min/1.73m²), and 95% confidence intervals.

Specific Aim 2 Sample size justification: We will

enroll 280 eligible patients from Specific Aim 1 for 1:1 randomization in our RCT for Specific Aim 2. Based on our prior experience with ongoing RCTs in the study location, we anticipate that enrollment into Aim 2 will take 12 months and there will be 10% loss to follow up at end of year 2, yielding 252 patients on study (126 per arm). Aim 2A: At 2 years, we hypothesize that a higher proportion of intervention participants will regress from microalbuminuria to normoalbuminuria (uACR < 30 mg/g) with a hazard ratio (HR)= 2.50. Using the logrank test, we will have approximately 80% power if the rate of regression in the SOC arm is at least 12%, and 90% power if that rate is 16% or higher with a 1.7% type I error¹³⁶. (The type I error rate was set at 5%/3=1.7% to account for multiple testing and the fact that we have 3 primary endpoints.) See Tables 3 and 4. Aim 2B: At 2 years, we hypothesize that a higher proportion of patients in the SOC arm. namely 60% vs. 25% in the intervention arm (HR≈0.42), will progress from microalbuminuria to macroalbuminuria (uACR > 300 mg/g). With 126 patients per arm (after removing 10% loss to follow-up), we will have >95% power for Aim 2B with a 1.7% type I error. See Tables 5 and 6. Figure 3 shows changes in Aim 2A power for varying SOC regression rates and changes in Aim 2B power for varying sample size. The sample size for Aim 2C is such that we will have approximately 80% power to detect at the alpha=0.017 level a difference in the log-transformed mean uACR of 0.24, which is approximately 0.41 standard deviations. These power calculations are likely conservative, as they do not incorporate baseline covariates, which will be included in the actual analyses (see below) and should improve power; in addition, the uACR analysis will incorporate multiple longitudinal measures per person whereas these power calculations only assume a single final measurement per person.

The sample size was chosen to have sufficient power for all primary endpoints. Tables S1-S8, investigating power and detectable alternatives for the secondary endpoints with a total sample size of 280 are provided in Appendix B. In short, we anticipate low power to detect differences between intervention arms in the doubling of serum creatinine, all-

cause mortality, and tenofovir toxicity because the expected rates for these events in the placebo arm are anticipated to be small (i.e., 2-20%, <10%, and 2%, respectively). We should have sufficient power to detect meaningful differences in eGFR, quality of life scores, and blood pressure.

alpha	Events Needed	Approx Rate SOC	Approx Rate Exp	Patients per Arm	Power
0.010	38	0.12	0.3	100	0.595
0.010	50	0.16	0.4	100	0.751
0.010	45	0.12	0.3	120	0.695
0.010	60	0.16	0.4	120	0.838
0.010	53	0.12	0.3	140	0.775
0.010	71	0.16	0.4	140	0.898
0.010	60	0.12	0.3	160	0.838
0.010	81	0.16	0.4	160	0.938
0.010	68	0.12	0.3	180	0.886
0.010	91	0.16	0.4	180	0.963
0.017	38	0.12	0.3	100	0.666
0.017	50	0.16	0.4	100	0.807
0.017	45	0.12	0.3	120	0.758
0.017	60	0.16	0.4	120	0.880
0.017	53	0.12	0.3	140	0.828
0.017	71	0.16	0.4	140	0.928
0.017	60	0.12	0.3	160	0.880
0.017	81	0.16	0.4	160	0.958
0.017	68	0.12	0.3	180	0.918
0.017	91	0.16	0.4	180	0.976
0.025	38	0.12	0.3	100	0.717
0.025	50	0.16	0.4	100	0.844
0.025	45	0.12	0.3	120	0.801
0.025	60	0.16	0.4	120	0.907
0.025	53	0.12	0.3	140	0.862
0.025	71	0.16	0.4	140	0.946
0.025	60	0.12	0.3	160	0.907
0.025	81	0.16	0.4	160	0.969
0.025	68	0.12	0.3	180	0.938
0.025	91	0.16	0.4	180	0.983
0.050	38	0.12	0.3	100	0.804
0.050	50	0.16	0.4	100	0.902
0.050	45	0.12	0.3	120	0.870
0.050	60	0.16	0.4	120	0.946
0.050	53	0.12	0.3	140	0.915
0.050	71	0.16	0.4	140	0.971
0.050	60	0.12	0.3	160	0.946
0.050	81	0.16	0.4	160	0.984
0.050	68	0.12	0.3	180	0.966
0.050	91	0.16	0.4	180	0.992

Table 3. Power calculation for regression

For these calculations, an HR of 2.5 was assumed.

Table 4. Detectable hazard ratios (HR) for regression

alpha	Events	Approx	Approx	Patients	Detectable
	Needed	Rate SOC	Rate Exp	per Arm	HR
0.010	42	0.12	0.35	100	2.88
0.010	52	0.16	0.41	100	2.59
0.010	48	0.12	0.32	120	2.69
0.010	59	0.16	0.39	120	2.43
0.010	54	0.12	0.31	140	2.54
0.010	67	0.16	0.37	140	2.31
0.010	59	0.12	0.29	160	2.43
0.010	74	0.16	0.35	160	2.21
0.010	65	0.12	0.28	180	2.34
0.010	81	0.16	0.34	180	2.13
0.017	41	0.12	0.33	100	2.76
0.017	50	0.16	0.40	100	2.49
0.017	46	0.12	0.31	120	2.58
0.017	58	0.16	0.37	120	2.34
0.017	52	0.12	0.29	140	2.45
0.017	65	0.16	0.36	140	2.23
0.017	58	0.12	0.28	160	2.34
0.017	72	0.16	0.34	160	2.14
0.017	63	0.12	0.27	180	2.25
0.017	79	0.16	0.33	180	2.06
0.025	40	0.12	0.32	100	2.66
0.025	49	0.16	0.39	100	2.41
0.025	45	0.12	0.30	120	2.50
0.025	57	0.16	0.36	120	2.27
0.025	51	0.12	0.28	140	2.37
0.025	64	0.16	0.35	140	2.16
0.025	57	0.12	0.27	160	2.27
0.025	71	0.16	0.33	160	2.08
0.025	62	0.12	0.26	180	2.19
0.025	78	0.16	0.32	180	2.01
0.050	38	0.12	0.30	100	2.49
0.050	47	0.16	0.36	100	2.26
0.050	43	0.12	0.28	120	2.34
0.050	54	0.16	0.34	120	2.14
0.050	49	0.12	0.27	140	2.23
0.050	61	0.16	0.33	140	2.04
0.050	54	0.12	0.26	160	2.14
0.050	68	0.16	0.32	160	1.97
0.050	60	0.12	0.25	180	2.07
0.050	75	0.16	0.31	180	1.91

For these calculations, a power of 80% (0.80) was assumed.

Table 5. Power calculation for progression

alpha	HR	Progression events	Patients per arm	Power
0.010	0.42	76	100	0.895
0.010	0.42	92	120	0.947
0.010	0.42	107	140	0.975
0.010	0.42	122	160	0.988
0.010	0.42	138	180	0.995
0.017	0.42	76	100	0.925

0.017	0.42	92	120	0.965
0.017	0.42	107	140	0.984
0.017	0.42	122	160	0.993
0.017	0.42	138	180	0.997
0.025	0.42	76	100	0.944
0.025	0.42	92	120	0.975
0.025	0.42	107	140	0.989
0.025	0.42	122	160	0.995
0.025	0.42	138	180	0.998
0.050	0.42	76	100	0.969
0.050	0.42	92	120	0.987
0.050	0.42	107	140	0.995
0.050	0.42	122	160	0.998
0.050	0.42	138	180	0.999

For these calculations, we assumed HR=0.42, approximate rate of progression in the SOC arm=0.6, and approximate rate of progression among those on the experimental arm=0.25.

	. Delectable	Παζαια ιαι	los for progr	5331011
alpha	Progression Events	Approx. Rate Exp	Patients per Arm	HR
0.010	79	0.28	100	0.46
0.010	97	0.30	120	0.50
0.010	116	0.32	140	0.53
0.010	134	0.33	160	0.55
0.010	153	0.35	180	0.58
0.017	80	0.29	100	0.49
0.017	99	0.31	120	0.52
0.017	117	0.33	140	0.55
0.017	136	0.34	160	0.57
0.017	155	0.36	180	0.60
0.025	81	0.30	100	0.50
0.025	100	0.32	120	0.54
0.025	119	0.34	140	0.57
0.025	137	0.35	160	0.59
0.025	157	0.37	180	0.61
0.050	83	0.32	100	0.54
0.050	102	0.34	120	0.57
0.050	121	0.36	140	0.60
0.050	140	0.37	160	0.62
0.050	160	0.39	180	0.64

Table 6.	Detectable	hazard ratios	for progression
----------	------------	---------------	-----------------

For these calculations, we assumed a power of 80% (0.80) and an approximate rate of progression in the SOC arm of 60% (0.6).

Statistical analysis plan: Our first approach will be to perform an intent-to-treat analysis, but we will also perform an on-treatment analysis to compare these data and present all available findings. *Primary analysis*: We will test the hypotheses that regression and progression rates are different across arms using multivariable Cox regression models with the intervention variable (randomization to RAAS [yes/no]) as the primary predictor variable, adjusting for baseline (pre-randomization) covariates including baseline uACR, *APOL1* renal risk variants, CD4+ cell count, blood pressure

ART regimen (DTG vs. other), and the presence/absence of comorbid medical conditions (hypertension, cardiovascular disease). To relax linearity assumptions, baseline uACR will be included in models using restricted cubic splines.¹³⁸ Primary analyses will be intention to treat, although we also plan to perform "per protocol" analysis. We will also test the impact of study arm on uACR using a linear mixed effects model to account for within patient correlation with the outcome of 3-monthly uACR values (with primary endpoints obtained by evaluating the uACR and other key renal outcomes at 18 and 30 months given that all enrolled study participants will not be placed or sustained on their maximum tolerated lisinopril dose or matched placebo until 6 months after study enrollment). The model will also adjust for the baseline covariates given above. For this analysis, we anticipate log-transforming uACR to meet modelling assumptions, although other transformations will be considered if needed.

Secondary analyses: Analyses for secondary endpoints will be similar to that described above. Time-to-event outcomes (doubling of serum creatinine from baseline, all-cause mortality, 40% decline in eGFR, and tenofovir toxicity) will be assessed using multivariable Cox regression models. Continuous outcomes (eGFR, quality of life metrics, and blood pressure) will be analyzed using mixed effects models after proper transformation of the outcome variable, if necessary. Baseline covariates listed above will be included in all secondary analyses.

In conversations with the DSMB, concerns were brought up regarding the nationwide switch to dolutegravir (DTG) and its potential impact on results. As sensitivity analyses, we will repeat the primary and secondary analyses listed above but also include any switch to a DTG-containing regimen post-randomization as a time-varying covariate. Our rationale for not including DTG-switch in the primary analysis, is that post-randomization variables (such as a switch to DTG) could be affected by treatment assignment and adjusting for it could therefore potentially bias results. However, we believe that the transition to DTG will not be affected by treatment assignment, in which case these analyses will be fine. If post-randomization DTG-uptake does differ by treatment arm (>5%), then we will investigate whether DTG-use is a mediator between treatment assignment and any of the primary or secondary outcomes listed above. Mediation analyses will follow the approaches outlined in VanderWeele TJ (2015) Explanation in Causal Inference. Finally, we will investigate whether the effect of assignment to ACEi could be modified by DTG-use. To do this, we will repeat the primary and secondary analyses but include an interaction between time-varying DTG-use and treatment assignment.

Potential difficulty reaching desired sample size: Our microalbuminuria prevalence estimates among HIV positive adults engaged in care at AKTH are conservative, as they are based on published data from this same hospital among asymptomatic HIV positive adults, and we anticipate that only approximately 59% of those eligible for our aim 2 study will need to consent/enroll in order for us to reach our target sample sizes. Therefore, with a target sample size equal to 280, 59% of eligible patients would need to consent for Study Aim 2.

Retention Strategies: To increase the likelihood of retention in the trial, we plan to use several evidence-based methods that have been effective in clinical trials. The use of simple, clear, detailed written and verbal instructions regarding therapy, possible treatment side effects, and tests required for the study increases comprehension of the purpose and importance of the study, and yields better adherence to the trial.¹³⁷⁻¹⁴⁰ In terms of specifics: i) We will develop a brochure outlining the study protocol in simple terms that will be translated into Hausa (native language of majority of individuals that live in Kano, Nigeria); ii) the key to successful follow-up and retention will be attention to detail, consistency of the research team, and trust between participants and study and clinic staff. The research staff will contact participants immediately and reschedule appointments when missed; iii) Close monitoring of participants' visits and need for return appointments with follow-up telephone calls are key elements for monitoring patient attendance and prevention of loss to follow-up. Every attempt will be made by the study team to contact participants prior to their scheduled visit based on the study schedule: and iv) identification of a trusted contact person who does not live with the study participant but always knows the participant's whereabouts will assist in tracking participants at risk of loss to follow-up and will decrease attrition. NOTE: The AKTH HIV clinic has historically had high retention rates. In a recent 10 year prospective cohort study conducted by our team (29,860 person-months of follow-up), 83% of our patients in the cohort were still in care after 10 years.¹⁴¹ We will employ the same retention initiatives that have been shown to be effective in our study setting, including: active engagement of peer mentors in recruitment, counseling and monitoring activities, community involvement, supportive home-based care services, early case detection, and close tracking of at-risk persons with missed visits.

Specific Aim 3

Statistical analysis and considerations: Analyses for Aim 3 will be the same as those outlined in Aim 2, except the predictor of interest will be APOL1 haplotype (high risk vs. low risk) instead of intervention arm; analyses will adjust for intervention arm (similar to how analyses of Aim 1 adjusted for APOL1 genotype). Assuming that ~30% (n = 84) of Aim 2 study participants have the high risk genotype, namely 2 copies of the risk variants (G1/G1, G1/G2, or G2/G2), with the remainder of Aim 2 study participants (n =196) having the low risk genotype (carrying no or one risk allele [G0/G0, G0/G1, and G0/G2]), and that the rate of progression will be similar to that hypothesized in Aim 2, we anticipate having 80% power to detect hazard ratios on the order of 2.4 to 3.2. Specifically, if the rate of regression is 22% (e.g., 10% and 25% in the SOC and intervention arms, respectively), we will have 80% power to detect a hazard ratio of 3.2 between the low and high risk genotypes; if the rate of regression is 35% (e.g., 20% and 40% in the SOC and intervention arms, respectively), we will have 80% power to detect a hazard ratio of 2.4. With regards to progression, if the overall event rate is 42.5%, we anticipate having 80% power to detect a hazard ratio of 2.1 between the high and low risk genotypes; if the overall rate of progression is 28%, we anticipate approximately 80% power to detect a hazard ratio of 2.5. Analyses will be repeated treating number of risk alleles (0, 1, or 2) as a categorical variable to investigate differences in risks when having 0 vs. 1 risk allele.

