NOTE: Although the eligible population of the HIV clinic at AKTH is 40% male, we anticipate that females will be more likely to enroll in this study, given our previous experience. Therefore, study staff will specifically target males for enrollment in order to achieve a gender balance in our study enrollment. Strategies that will be utilized by staff include use of male counselors in the clinic, utilization of male peer counselors for targeted recruitment, and extension of clinic hours to accommodate male participants who may not be able to attend otherwise due to work engagements. These strategies have all been utilized successfully by our team in previous studies and HIV scale-up efforts within Nigeria and Mozambique.¹¹⁸⁻¹²⁰ In addition, given preliminary Aim 1 data, with the mean duration of ART among enrolled aim 1 participants being > 8 years, strategies will be utilized by staff to prioritize the identification of persons more recently (within the past 6-24 months) in order to enroll a large cohort of HIV-positive adults with a more balanced duration of time on ART. Lastly, also given preliminary Aim 1 data review coupled with DSMB feedback (January 23, 2019), it was seen that ~ 75% of enrolled aim 1 participants (n = 380) had a self-reported ethnicity of Hausa/Fulani; with only \sim 4-5% self-reporting their ethnicity as Yoruba. Based on published literature to date^{39,40}, carriage of the *APOL1* high risk (HR) genotype has been shown to be highest among persons of Yoruba descent and other ethnic groups (i.e. lgbo) and more prevalent in the southern part of Nigeria. To address this in order to increase enrolment of persons of Yoruba descent, we will plan to open a second study site; namely the Infectious Disease Hospital that is also in Kano, as the demographics of the population this hospital serves is guite different when compared to AKTH in that they service significantly higher proportions of persons of Yoruba and other ethnicities from southern Nigeria; where proportions of the population possessing the APOL1 HR genotype are highest^{39,4039-40}.

Inclusion and exclusion criteria to be used for participant enrollment into Study Aim 2 are shown below.

Inclusion criteria:

- Participated in Study Aim 1: prevalence of *APOL1* high risk status and clinical correlates

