5.0 Study Procedures

Aim 1 Study Procedures

Each consenting patient will have a full medical evaluation and will provide two firstmorning void urine specimens (5 mL) because of variability. We will measure urinary albumin and creatinine levels to calculate a mean (2 sample) uACR value. The second first-morning uACR will be obtained 4-8 weeks after the first specimen. Assays will be performed using the Roche Hitachi Cobas C 311 (Roche Diagnostics Indianapolis, IN) system, using pyrogallol red urine creatinine by a kinetic Jaffe method and urine albumin by immunoturbidimetry.^{121,122} Each consenting patient will also provide one blood sample for serum creatinine and cystatin C, from which we will calculate eGFR using the CKD epidemiology collaboration (CKD-EPI-Cr-CyC)^{123,124} equation. NOTE: We will use both serum cvstatin C¹²⁵ and CKD-EPI^{123,124} to calculate eGFR. Although the CKD-EPI equation is preferred/more accurate, Shlipak et al.¹²⁵ have shown that the use of both serum cystatin C and serum creatinine for eGFR estimations strengthens the association between eGFR and the risk of ESKD and death across diverse populations. During their first AKTH clinic visit, all screened patients will have their confirmatory HIV-1 ELISA test result as well as the most recent CD4+ count and viral load results obtained from their medical records/charts, per existing standard-of-care. Each screened patient will be given a unique study ID number, which the study team will maintain. The study ID can be linked back to individual patients (and will therefore be kept in a locked cabinet - all information linking patients to ID numbers will be destroyed once study follow-up for Aims 1-3 is complete). Individual patient data that will be collected and maintained by de-identified study ID include: age, race/ethnicity, sex, weight, BMI, and comorbid medical conditions (prior/current opportunistic infections, syphilis, cancer, hypertension, other cardiovascular diseases).

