CA) targeting the 3 chromosome 22 APOL1 variants (rs73885319 [G1], rs60910145 [G1], and rs 71785313 [G2]) associated with CKD and HIV-associated kidney disease. The APOL1 risk alleles are defined by the G1 haplotypes (rs73885319-G/rs60910145-G and rs73885319-G/rs60910145-T) and by the G2 haplotype (rs71785313-deletion). We will infer the APOL1 genotype from the number of risk alleles: individuals exhibiting two risk alleles (G1/G1, G1/G2, or G2/G2) will be assigned to the "high-risk (HR)" group, while individuals carrying no or one risk allele (G0/G0, G0/G1, and G0/G2) will be attributed to the "low-risk (LR)" group. We will also examine the risk allele groups in a categorical manner (0 vs. 1 vs. 2 alleles and 0 vs. 1 risk alleles) to determine whether presence of a single risk allele poses increased risk. We will then determine the overall prevalence of APOL1 risk alleles, including odds ratios for baseline CKD and albuminuria, and the standard error for beta comparing levels of microalbuminuria and eGFR stratified by genotype (including testing for association between the APOL1 genotype and longitudinal eGFR slope using linear regressions). In addition, we will perform crude and adjusted linear regression analyses (modified Poisson regression) to test for associations with mean uACR, eGFR, and CKD, adjusting for sex, blood pressure, and age. Based on previous genetic association work in HIVAN, we will test both additive and recessive genetic models to capture all potential risk alleles associated with microalbuminuria and CKD. Because of the strong associations reported for APOL1 with HIVAN (OR=29, U.S. and OR 89, South African, recessive model), our cohort exhibits substantial power to detect the effects of APOL1 in the recessive model. For APOL1, we anticipate that 12% of controls and 36% of cases will carry the APOL1 HR genotype; this is a strong epidemiological association, but modest on the scale of known effects of APOL1 risk alleles on kidney disease.

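### The APOL1 genotype models in Aims 1 and 3 do not pre-specify self-reported ethnicity or enrolling site, although the protocol itself links genotype frequency to ethnicity and plans to change the ethnic mix

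*Combined protocol and SAP*

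**What the plan says.** Covariates for the genotype models are described in four places.

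- **Section 8.0, Specific Aim 1, linear models for log10 uACR and eGFR:** these will "adjust for potential confounders, including: sex, age, CD4+ cell count, viral load, and the presence/absence of specific comorbid medical conditions".
- **Section 8.0, Specific Aim 1, binary outcomes:** "Poisson regression adjusted for similar variables, will be used to assess associations with prevalent CKD, microalbuminuria, and reduced eGFR".
- **Section 5.0, Genetics specimen collection and analysis, on the same associations:** "adjusting for sex, blood pressure, and age".
- **Section 8.0, Specific Aim 3:** "Analyses for Aim 3 will be the same as those outlined in Aim 2, except the predictor of interest will be APOL1 haplotype", and "analyses will adjust for intervention arm". The Aim 2 covariates taken over are baseline uACR, APOL1, CD4+ count, blood pressure, ART regimen (DTG or other) and comorbid conditions.

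The first association test listed for Aim 1 is an unadjusted Wilcoxon rank sum test.

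On ethnicity, the recruitment text in Section 3.0 says that high-risk carriage "has been shown to be highest among persons of Yoruba descent and other ethnic groups". It reports that about 75% of early Aim 1 enrollees (n = 380) were Hausa/Fulani and about 4-5% Yoruba. It plans a second Kano hospital because "they service significantly higher proportions of persons of Yoruba and other ethnicities from southern Nigeria". The Background puts the risk-allele frequency above 50% in Yoruba and Igbo. Section 5.0 says that the individual data to be collected "include: age, race/ethnicity, sex, weight, BMI, and comorbid medical conditions". Ethnicity is therefore recorded, but it has no stated role in the analysis.

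**The concern.** In Aims 1 and 3 the exposure is genotype, which nobody randomises. Stratifying the Aim 2 randomisation by number of risk alleles balances treatment arms within genotype. It does not balance ethnicity across genotypes. Recruitment was changed after DSMB feedback because genotype depends on ethnicity, but that dependence was not carried into the analysis. If the second hospital opens as intended, genotype, ethnicity and site will be correlated by design.

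The planned assays cover only three APOL1 variants, so no genetic ancestry adjustment can stand in for self-reported ethnicity. Any ethnic or site difference in albuminuria or eGFR that arises for other reasons, and that the listed covariates do not capture, would be read as an APOL1 effect or would mask one. The protocol expects these results to inform treatment guidelines.

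**Working it through.** **1. The plan's own Aim 1 figure.** Section 8.0 gives 90% power for a relative risk (RR) of 1.37, with N = 2,600, microalbuminuria prevalence 17.5% and 1 in 4 carrying the risk genotype. I assume two-sided alpha 0.05, since none is stated.
- Low-risk prevalence: 0.175 / (0.75 + 0.25 × 1.37) = 0.160. High-risk prevalence: 1.37 × 0.160 = 0.219.
- With 1,950 and 650 participants, a two-proportion test has 91.9% power. The stated figure reproduces and is not in dispute.

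**2. Covariate lists side by side.**

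| Analysis | Named covariates | Ethnicity | Site |
|---|---|---|---|
| Aim 1, Section 8.0 | sex, age, CD4+, viral load, comorbidities | no | no |
| Aim 1, Section 5.0 | sex, blood pressure, age | no | no |
| Aim 3, Section 8.0 | Aim 2 set plus intervention arm | no | no |

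**3. Illustration of possible size (crude Aim 1 comparison, no true APOL1 effect).** Take two groups, a majority and a southern group. Let s be the southern share, hN and hS high-risk carriage in the majority and southern groups, r the southern-to-majority prevalence ratio for microalbuminuria, and M = 0.175 overall.
- Prevalence: mN = M / ((1 − s) + s·r); mS = r·mN.
- Overall carriage: H = (1 − s)·hN + s·hS.
- High-risk genotype: P1 = [(1 − s)·hN·mN + s·hS·mS] / H.
- Low-risk genotype: P0 = [(1 − s)(1 − hN)·mN + s(1 − hS)·mS] / (1 − H).
- Spurious RR = P1 / P0.

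The documents supply M. They also support hS of about 25%: an allele frequency of 50% gives 0.5² = 0.25 under Hardy-Weinberg. Values for hN and r, higher values of hS, and the eventual s are assumptions.

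*Example A:* s = 0.25, hN = 0.05, hS = 0.25, r = 2.
- mN = 0.175 / 1.25 = 0.140; mS = 0.280; H = 0.10.
- P1 = (0.00525 + 0.0175) / 0.10 = 0.2275; P0 = (0.09975 + 0.0525) / 0.90 = 0.1692; RR = 1.345.
- With r = 0.67 instead, RR = 0.852.

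*Example B, overall carriage at the planned 25%:* s = 0.5, hN = 0.10, hS = 0.40, r = 2.
- mN = 0.175 / 1.5 = 0.1167; mS = 0.2333.
- P1 = (0.00583 + 0.04667) / 0.25 = 0.210; P0 = (0.0525 + 0.0700) / 0.75 = 0.1633; RR = 1.29.
- With hN = 0.15, hS = 0.35 and r = 1.3, H is again 0.25 and RR = 1.07.

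| Assumed range | Spurious crude RR |
|---|---|
| hN 5-15%, hS 25%, s 5-50%, r 0.67-2.0 | about 0.84 to 1.35 |
| Same, s fixed at 5% (close to the early Yoruba share) | 0.94 to 1.16 |
| H within about 1.25 points of 25%; hN 5-15%, hS 30-40%, s 25-50%, r 1.3-2.0 | about 1.06 to 1.32 |
| r = 1, any shares | 1.00 |

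In the first row, overall carriage never exceeds 0.5 × 0.15 + 0.5 × 0.25 = 20%, below the plan's 1 in 4. In the third row the upper limit depends on how tightly overall carriage is held: at 23% (hN = 0.06, hS = 0.40, s = 0.5, r = 2) it is 1.35. That row covers only ratios above 1. In every scenario the RR within each group is 1.00, so stratifying on group removes the bias.

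**The case against.** The strongest reply has four parts.

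- **The lists are open.** The Section 8.0 lists for Aims 1 and 2 are introduced as inclusive, and the Poisson models use similar variables, so ethnicity and site are not ruled out. That stands: a reader might infer that they are excluded, and the text does not say so. Only the Section 5.0 list reads as closed. Leaving the choice open still means it could be made after the genotype results are known.
- **A necessary premise is missing.** Bias needs kidney outcomes to differ by ethnicity or site for reasons other than APOL1. The documents report no such difference. That stands, and it limits what can be claimed about size.
- **Some routes are already covered.** Blood pressure is in the Section 5.0 and Aim 3 sets, hypertension is among the Aim 1 comorbidities, and ART regimen is in Aim 3. One analyser system is named for the urine assays. That stands in part: diet, duration of ART and specimen handling have no covariate or stated control.
- **The second site is only planned.** Sections 4.0 and 6.0 still name one hospital. That stands for site. It does not answer the ethnicity point, because about 25% of early enrollees were already not Hausa/Fulani.

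**Conclusion.** The point holds as a gap in pre-specification. No named covariate set for the Aim 1 or Aim 3 genotype models contains ethnicity or site, although the protocol ties genotype to ethnicity and plans to shift the ethnic mix. That part is certain. Whether bias follows, how large it is and in which direction cannot be determined from the documents.

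A reader might infer from the illustration that a spurious RR near the 1.37 target is likely. The documents do not support that. The calculation is a crude comparison, whereas the planned binary-outcome analysis is an adjusted Poisson model. The inputs that drive it are assumed. With overall carriage near the plan's 25%, the crude figure tops out at about 1.3. There is no corresponding figure for Aim 3, whose covariates may remove part of any confounding.

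Nor should the point be extended to Aim 2. Treatment there is randomised, and the lisinopril-placebo comparison is not confounded in this way.

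**What to change.** 1. Pre-specify self-reported ethnicity, grouped for example as Hausa/Fulani, Yoruba, Igbo and other, in every Aim 1 and Aim 3 genotype model. Add enrolling site if the second hospital opens.
2. Use one covariate set for the Aim 1 genotype models in Sections 5.0 and 8.0.
3. Base the Aim 1 conclusion on the adjusted estimate and keep the Wilcoxon test as descriptive. Section 8.0 does not currently say which is primary.
4. Report genotype prevalence and the genotype associations by ethnicity. A pooled prevalence will depend on how far recruitment is enriched.

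The cost is a few degrees of freedom, small at N = 2,600 and modest at N = 280. Ethnicity is already collected, and enrolling site would be known for each participant. No extra visits or assays are needed.
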